### **Evaluation of the Practice Facilitation Intervention: Implementation and Clinical Outcomes.**

Aim 3 implementation and clinical-specific outcomes were derived guided by the RE-AIM (Reach, Effectiveness, Adoption, Implementation, and Maintenance) evaluative framework, often used to guide implementation evaluations. RE-AIM will be assessed using EHR data pulled from VA's Corporate Data Warehouse (CDW). The data pull will include data from January 1, 2019 – December 31, 2023, to evaluate these outcomes, which includes the pre-intervention period, the active facilitation intervention period, and the post-facilitation intervention period (i.e., 3-, 6-, and 12-months after active implementation). RE-AIM constructs are defined as follows:

**Reach** of alcohol-related care will be assessed at the patient level using EHR data, pulled from VA's CDW. **Reach** outcomes will be expressed as a rate, with the

denominator (for all outcomes) defined as all Veterans with a visit to the Pittsburgh VA primary care clinic during the practice facilitation intervention. The numerator for each Reach outcome is as follows: the number of Veterans who screened positive for unhealthy alcohol use (AUDIT-C  $\geq$  5) AND had any documented brief intervention, encounters with primary care-mental health integration (PC-MHI), encounters with PACT/ Whole Health clinical pharmacists, specialty addictions treatment (inpatient and outpatient clinic visits for substance use disorder treatment encounters with an accompanying AUD diagnosis), or pharmacotherapy for AUD (any filled prescription for FDA-approved medications: acamprosate, disulfiram, or oral/injectable naltrexone or non-FDA approved effective medications: gabapentin, baclofen, or topiramate) in the 30 days following a positive screen. Denominators will also be derived to represent specific subpopulations (e.g., women, Black and Hispanic Veterans). Rates at the start of the practice facilitation intervention and at 3- and 6-months post intervention will be calculated to examine change in Reach outcomes over time.

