## **5.2 Recruitment Methods**

Ann Arbor regulatory approval is being requested only for the data analysis portion of AIM 3 (extraction, cleaning, and analysis of AIM 3 outcome data from the VA's electronic health record via the Corporate Data Warehouse). All recruitment, enrollment and intervention activities were completed at the Pittsburgh VA.

Approximately 10,000 Veterans' data will be pulled from the CDW to examine implementation and clinical outcomes. Data to evaluate implementation and clinical effectiveness outcomes will be obtained electronically and securely from already collected administrative databases, using scrambled SSN or Patient ICN to link data together. Data sources will include the CDW, Health Factors (AUDIT-C and Brief Intervention information), Vital Status File to obtain DOB for calculating age of Veterans, and Prescription/Pharmacy information (for data on whether medications for alcohol use disorder were prescribed). Other specific records include: sociodemographics (e.g., sex, gender identity, marital status, indicator of socioeconomic status, race/ethnicity, sexual orientation), past-year diagnoses (Alcohol use disorder diagnosis, Substance use disorder diagnoses, Tobacco use disorder diagnosis, Mental Health disorder diagnosis (Depression, anxiety, PTSD, Bipolar, Psychotic-spectrum)), index of medical complexity (e.g., Charlson index, VA CAN score) utilization of primary care services pre-implementation (2019-2022), during (July 2022 - Dec. 2022) and post-implementation intervention (Jan 2023 - Dec. 2023), referral and utilization of substance use services in the past year (yes/no), and referral and utilization of past-year mental health services (yes/no). Data may also be reviewed within CAPRI/Joint Legacy Viewer (JLV) to allow study team members to look into potential data anomalies from our dataset. In addition, members of the study team may review notes, charts, dates of AUDIT-C administration, etc. to verify the accuracy of our Aim 3 dataset.

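### The Reach numerator counts some fills and encounters as alcohol care whatever their reason, so Reach should also be reported by component and in an alcohol-specific version

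*Combined protocol and SAP*

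**What the plan says.** The Reach definition is in section 5.1, under Evaluation of the Practice Facilitation Intervention. The numerator starts from "the number of Veterans who screened positive for unhealthy alcohol use (AUDIT-C" score of 5 or more) and then requires any one of these, "in the 30 days following a positive screen":

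- a documented brief intervention;
- "encounters with primary care-mental health integration (PC-MHI");
- "encounters with PACT/ Whole Health clinical pharmacists";
- specialty addictions treatment, defined as "substance use disorder treatment encounters with an accompanying AUD diagnosis";
- "pharmacotherapy for AUD (any filled prescription for FDA-approved medications: acamprosate, disulfiram, or oral/injectable naltrexone" or "non-FDA approved effective medications: gabapentin, baclofen, or topiramate").

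The specialty item is the only one with a diagnosis condition. No item has a look-back rule that would separate a new prescription from a refill.

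Section 5.2 requests pharmacy data and "past-year diagnoses (Alcohol use disorder diagnosis, Substance use disorder diagnoses" among others), and it permits chart checks of data accuracy. It does not connect either to the Reach numerator. Section 5.7 reports Reach descriptively, compares 2019-2022 with 3 and 6 months after the intervention, and adds no restriction or sensitivity analysis. Reach is used again at 12 months for Maintenance.

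**The concern.** Reach is meant to show how many Veterans with unhealthy alcohol use received alcohol-related care after a positive screen. Three of the five components can be met by care that has nothing to do with alcohol.

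The documents themselves point to this. The plan labels the three added drugs as not FDA-approved for this use. PC-MHI is by name a mental health service, and section 5.2 pulls depression, anxiety, PTSD, bipolar and psychotic-spectrum diagnoses for the same Veterans. That the three drugs are commonly taken for other conditions, and that clinical pharmacists see patients for other reasons, is general clinical knowledge and is not stated in the plan. A refill of a drug started well before the screen also satisfies the rule as written.

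What is at stake is the reading of the before-after comparison. Unrelated care adds a background that facilitation is not aimed at, and that background may change for reasons of its own. Because Maintenance reuses Reach, any error carries into it. Medication is the most exposed component, and section 5.1 says training on AUD medications was offered as part of facilitation.

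**Working it through.** The plan states no baseline Reach, target change, power or background rate, so there is no figure to reproduce. The steps below show direction and form. Every rate in them is an assumption.

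**Model.** Among screen-positive Veterans, let p be the share who truly receive alcohol care within 30 days. Let b be the share who would meet the definition through unrelated care, independently of p. For an any-of numerator:

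- measured Reach = p + (1 - p)b
- overstatement = (1 - p)b
- measured change with b constant = (p1 - p0)(1 - b)

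**Constant background, assumed true rise from 30% to 40%:**

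| b | Before | After | Change | Ratio |
|---|---|---|---|---|
| 0 | 30% | 40% | 10 points | 1.33 |
| 10% | 0.30 + 0.70 × 0.10 = 37% | 0.40 + 0.60 × 0.10 = 46% | 9 points | 1.24 |
| 20% | 0.30 + 0.70 × 0.20 = 44% | 0.40 + 0.60 × 0.20 = 52% | 8 points | 1.18 |
| 30% | 0.30 + 0.70 × 0.30 = 51% | 0.40 + 0.60 × 0.30 = 58% | 7 points | 1.14 |

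The overstatement runs from 0.60 × 0.10 = 6 points to 0.70 × 0.30 = 21 points. It is smaller when true Reach is high: at p = 60% to 70% and b = 10% it is 4 to 3 points.

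**Denominator.** The table is per screen-positive Veteran, as in the example in section 5.7. Section 5.1 instead divides by all Veterans with a clinic visit. On that scale every percentage and point difference is multiplied by the screen-positive prevalence, which is not given. At an assumed 10%, the 9- and 7-point changes become 0.9 and 0.7 points, and the overstatement becomes 0.6 to 2.1 points. At an assumed 20% these are 1.8 and 1.4 points, and 1.2 to 4.2 points. The ratios do not move.

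**Medication as its own outcome, assumed true rise from 5% to 10% of screen-positives, b now the share with an unrelated fill:**

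| b | Before | After | Ratio | Unrelated share of baseline count |
|---|---|---|---|---|
| 5% | 9.75% | 14.5% | 1.49 | 4.75 / 9.75 = 49% |
| 10% | 14.5% | 19% | 1.31 | 9.5 / 14.5 = 66% |
| 20% | 24% | 28% | 1.17 | 19 / 24 = 79% |

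The true ratio is 2.0.

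**Drifting background.** With p fixed at 40% and no true change, b moving from 10% to 15% gives (1 - 0.40) × 0.05 = +3 points, and the reverse gives -3 points. With a true rise from 30% to 40% and b falling from 30% to 20%, measured Reach goes from 51% to 0.40 + 0.60 × 0.20 = 52%, so a 10-point gain reads as 1 point.

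**The case against.** The case for leaving the definition alone has several parts.

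- The AUDIT-C threshold, the 30-day window and the label of pharmacotherapy for AUD all show intent and narrow the problem. They do narrow it, but the operational rule still accepts a fill for any reason, and the optional chart checks set no rule for deciding indication.
- Section 5.1 speaks of several Reach outcomes with a numerator for each, so the components may already be meant for separate reporting. That reading is open. Brief intervention and specialty treatment would then be clean, but medication, PC-MHI and pharmacist Reach would be affected more than the composite, as the second table shows.
- Section 5.1 also describes a comparison from the start of the intervention. Drift has less time there than against a 2019-2022 baseline. This is fair, but section 5.7 uses the longer baseline.
- Requiring a coded diagnosis has its own bias. The target is an AUDIT-C of 5 or more, not diagnosed AUD. Facilitation could change how diagnoses are coded, a past-year AUD diagnosis does not prove why a drug was filled, and a new-fill rule drops ongoing AUD treatment. This stands, and it is why the restricted definition should accompany the stated one and not replace it.
- Reach is descriptive, in a pilot, with no test or power target. This also stands and limits the severity.

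A reader might infer that Reach is overstated by 6 to 21 points, or that any true change must be diluted. The documents support neither. The first rests wholly on assumed rates and on the screen-positive denominator. The second needs a background that is constant and independent of alcohol care.

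**Conclusion.** The point holds as a weakness in how specific the measure is. As written, fills of the three non-approved drugs, including refills of drugs started before the screen, and PC-MHI and pharmacist encounters count as alcohol care whatever their reason. Nothing in sections 5.2 or 5.7 corrects this.

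The direction of the error in level is certain: unrelated care can only raise measured Reach. Its effect on the change is conditional. With b constant and independent of alcohol care, the change shrinks by the factor (1 - b). With b drifting between 2019-2022 and 2023, the error can go either way. The magnitude cannot be derived from the documents, because p, b and the screen-positive prevalence are all missing.

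It would go too far to conclude that the pilot's Reach result is invalid or that an AUD diagnosis must become the main criterion. Severity is should-fix: the harm is to the interpretation of a descriptive outcome.

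**What to change.** Before the analysis dataset is built, add to sections 5.1 and 5.7:

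1. Report each Reach component separately.
2. Report the composite as now defined and in one pre-specified alcohol-specific version. That version (a) either leaves out gabapentin, baclofen and topiramate or counts them only with a past-year AUD diagnosis and as a new fill after the screen, with the choice and the look-back length fixed in advance. It also (b) counts PC-MHI and pharmacist encounters only with an alcohol-related diagnosis on the encounter, if encounter diagnoses are available in the data pull.
3. State that Reach will be said to have increased only if the two versions agree. Apply the same reporting at 12 months for Maintenance.
4. State which denominator each figure uses.

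The cost is a little more analysis. Pharmacy records and past-year AUD diagnoses are already requested. Diagnoses on PC-MHI and pharmacist encounters are not explicitly listed in section 5.2 and need confirming. Data start on January 1, 2019, so any look-back is incomplete for screens early in that year. The restricted version misses uncoded alcohol care and ongoing treatment, and may shift if facilitation changes coding. Showing both versions makes those limits visible.

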**Adoption** is identified as the percentage of providers from the PC clinic who deliver alcohol-related care when a Veteran screens positive for unhealthy alcohol use. Specifically, we will use data available in the EHR to examine delivery of brief interventions, consults placed to PC-MHI/clinical pharmacists or specialty addictions treatment and providing pharmacotherapy for AUDs at the provider and clinic level. Rates of alcohol-related care pre-intervention (2019-2022), during the course of the practice facilitation intervention (July 2022-December 2022), after the intervention (e.g., 3- and 6-months post intervention (Jan 1, 2023-March 31, 2023, and Jan 1, 2023-June 30, 2023 respectively) will be used to measure whether adoption rates of alcohol-related care increased over time.

**Maintenance** is defined as the extent to which evidence-based alcohol care becomes routine and part of the PC culture (care sustained over time). Reach and Adoption outcomes using EHR data will be assessed at 12-months post intervention (Jan 1, 2023-Dec. 31, 2023) to examine whether high-quality alcohol care was sustained.

**Effectiveness** is defined as the prevalence of unhealthy alcohol use at 12-months post-intervention (Jan 1, 2023-Dec. 31, 2023) as measured by AUDIT-C scores pulled from the EHR. This variable will also be expressed as a rate with the denominator defined as all Veterans with a visit to PC during the practice facilitation intervention (same as for Reach outcomes). The numerator will be the number of Veterans with an encounter in PC who screened positive for unhealthy alcohol use (AUDIT-C  $\geq$  5) at 12-months post facilitation intervention. While it is unlikely that a pilot study will have a measurable

impact on clinical outcomes, measuring effectiveness will serve as pilot data for a larger trial.

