#### **5.7 Data Analysis**

**Implementation Outcomes:** Reach outcomes will be reported descriptively (e.g., percentage of patients with an AUDIT-C  $\geq 5$  who were offered a BI or pharmacotherapy for AUD) and compared pre- (2019-2022) and post-implementation (at 3- and 6-months) to see whether Reach of alcohol care increased over time. Adoption outcomes via EHR will be descriptive, and include percentages, frequencies, and means (SD) of alcohol-related care by provider and clinic to understand whether Adoption of high-quality alcohol-related care increased over time. Descriptives will be examined and compared at the start of Active Implementation and at 3- and 6-months post Active Implementation. Reach and Adoption rates will again be examined at 12-months post Active Implementation and compared to rates at 3- and 6-months to see if high-quality alcohol-related care was sustained (Maintenance). **Effectiveness outcomes:** Effectiveness will be assessed via a time-series analysis, where the intervention site will serve as its own control, and we will investigate whether Veterans' with an encounter in Pittsburgh VA Primary Care during the implementation intervention reduced their drinking 12-months post intervention using AUDIT-C scores in the EHR. Time-series analysis was chosen because historical trend is accounted for in the analytic model, results can be displayed graphically, and the size of the effect can be estimated at different times post

intervention. The outcome (AUDIT-C scores) will be modeled using a regression model with an indicator for practice facilitation (pre- vs. post-), a continuous term for time (days since practice facilitation dissemination) and the interaction between the two. The indicator variable will assess immediate changes in AUDIT-C scores post implementation intervention, while the interaction term will assess if there is a change in the slope of AUDIT-C scores pre- and intervention at 12-months. While there is controversy over whether pilot studies should assess clinical efficacy or effectiveness, we decided to examine it here as a training opportunity and as preparation for a possible hybrid effectiveness-implementation Merit trial investigating practice facilitation as a way to improve alcohol-related care on a larger scale.

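### No separate Reach rate is specified for the active facilitation months (July-December 2022), so Reach cannot separate no effect from an effect that faded once facilitation ended

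*Combined protocol and SAP*

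**What the plan says.** Section 5.1 (Evaluation of the Practice Facilitation Intervention) extracts data for 2019 to 2023, "which includes the pre-intervention period, the active facilitation intervention period, and the post-facilitation intervention period". For Reach it then names these time points: "Rates at the start of the practice facilitation intervention and at 3- and 6-months post intervention will be calculated to examine change in Reach outcomes". Reach uses a fixed population, a "denominator (for all outcomes) defined as all Veterans with a visit to the Pittsburgh VA primary care clinic during the practice facilitation intervention".

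Section 5.7 gives a different Reach comparison: "compared pre- (2019-2022) and post-implementation (at 3- and 6-months) to see whether Reach of alcohol care increased over time". Its example of a Reach percentage is taken among patients with AUDIT-C of 5 or more, not among everyone who visited.

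Maintenance adds a later point in section 5.1: "Reach and Adoption outcomes using EHR data will be assessed at 12-months post intervention (Jan 1, 2023-Dec. 31, 2023". In section 5.7 those rates are "compared to rates at 3- and 6-months to see if high-quality alcohol-related care was sustained (Maintenance").

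Adoption is handled differently. Section 5.1 plans Adoption rates before facilitation, after it, and also "during the course of the practice facilitation intervention (July 2022-December 2022"). The Adoption comparison in section 5.7 lists only the start of active implementation and 3 and 6 months afterwards, so the rate during facilitation is not carried over.

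**The concern.** Aim 3 asks whether facilitation improves the quality of alcohol-related care in primary care (Abstract, Methods). Reach is the patient-level measure of that. The facilitator observed care, held monthly meetings and supported improvement cycles between July and December 2022, yet every dated Reach follow-up begins on 1 January 2023, the day after that period ends.

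A flat Reach result therefore has two explanations that the listed rates cannot tell apart: facilitation did not change care, or it changed care and the change was lost when the facilitator left. The two point to different designs for the larger trial that sections 5.1 and 5.7 say this pilot prepares. Maintenance has the same gap: it has no active-period Reach level from which care could be said to be sustained.

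**Working it through.** The plan states no Reach rate, target effect, alpha or power, so there is no figure to reproduce. The check has two parts: the listed time points side by side, and arithmetic on assumed rates.

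**1. Time points listed**

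| Outcome and place | Before | During July-December 2022 | After |
|---|---|---|---|
| Reach, section 5.1 | Start of facilitation (no window given) | Not listed | 3 and 6 months |
| Reach, section 5.7 | 2019-2022 | Not listed | 3 and 6 months |
| Reach under Maintenance, 5.1 and 5.7 | None | Not listed | 12 months, against 3 and 6 |
| Adoption, section 5.1 | 2019-2022 | Listed | 3 and 6 months |
| Adoption, section 5.7 | Start of active implementation | Not listed | 3 and 6 months, then 12 |

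**2. Size of the understatement**

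Assume a baseline rate p0, an active-period rate p0 + d, and a gain that decays exponentially with half-life h months from 1 January 2023. With k = ln 2 / h, the mean share of d remaining over a post window of m months is

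(1 - exp(-k m)) / (k m).

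Example: h = 1 and m = 3 give k m = 3 x 0.693 = 2.079 and exp(-2.079) = 0.125, so the share is 0.875 / 2.079 = 0.42.

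| Half-life (months) | 3-month window | 6-month window | 12-month window |
|---|---|---|---|
| 0.5 | 24% | 12% | 6% |
| 1 | 42% | 24% | 12% |
| 3 | 72% | 54% | 34% |
| 6 | 85% | 72% | 54% |

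Complete loss by 1 January 2023 gives a share of zero.

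**3. Effect of a literal 2019-2022 baseline**

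The calendar years 2019-2022 hold 48 months, of which July-December 2022 is 6: 6/48 = 12.5%. Weighting months equally (an assumption), the baseline is (42 p0 + 6 (p0 + d)) / 48 = p0 + 0.125 d.

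Take p0 = 30% and d = 10 points, both assumed:

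- Baseline: (42 x 30 + 6 x 40) / 48 = 31.25%.
- Complete loss, post minus pre: 30 - 31.25 = -1.25 points, against 0 with a baseline ending in June 2022.
- Half-life 3 months, 3-month window: 7.2 - 1.25 = 6.0 points, against 7.2.
- Active minus pre, if it were reported with the baseline ending in June 2022: +10 points.

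With d = 20 points and complete loss, the listed contrast is 0 or -2.5 points, against +20 for active minus pre.

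These rates make sense only for the section 5.7 denominator of screen-positive patients. Under the section 5.1 denominator, a Reach of 30% would require at least 30% of all clinic visitors to screen positive.

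**4. Why the denominator matters to the remedy**

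Under section 5.1 the population is fixed: everyone in it has a visit in July-December 2022 by definition, but not necessarily in any other window. Write the rate as s x c, where s is the share of that population screening positive in a window and c is the share of those who receive care. If s in January-March 2023 is half its July-December 2022 value (an assumption) and c is unchanged, the rate halves. Adding an active-period column on the fixed population could thus show a rise and fall with no change in care.

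**The case against.** The strongest reply is that the active period is not absent from the evaluation. Its data are extracted to evaluate these outcomes, and the Reach population is defined by visits in it. The start of facilitation has no window and could take in early active months, and 2019-2022 read literally contains all of them. Section 5.1 also plans Adoption rates during facilitation, at provider and clinic level, covering brief intervention, consults and medication, so a rise could show there. Maintenance would reveal continuing fade: at a 3-month half-life and d = 10 points, the gain falls from 7.2 points in the 3-month window to 3.4 in the 12-month window. Finally, care that persists without the facilitator is a legitimate target, and an active-period average mixes ramp-up and possible observation effects with facilitation itself.

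Much of this stands. A reader might infer that Reach is never calculated for the active months and that a faded effect would be declared no effect of facilitation. The plan does not support that. Reach is descriptive with no decision rule, active data may already be blended into the comparator, Adoption covers part of the gap, and only near-immediate loss gives about zero.

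The gap itself remains. Blending active months into the comparator makes the contrast worse. Adoption is not a full substitute: its unit is the provider, it counts consults placed where Reach counts encounters, and section 5.7 omits its rate during facilitation. Maintenance shows fade after January 2023 but not the level from which care faded.

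**Conclusion.** The point holds in limited form. No separate Reach rate is specified for July-December 2022, and sections 5.1 and 5.7 disagree on the Reach comparator and on whether Adoption has a rate during facilitation. Reach on its own therefore cannot distinguish no effect from an effect that faded.

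Under assumed exponential decay, the 3-month window keeps 24% to 85% of the gain for half-lives of 0.5 to 6 months, and the 6-month window 12% to 72%. A literal 2019-2022 baseline removes a further 0.125 d. The baseline rate, effect sizes, half-lives and decay shape are all assumptions; the plan gives none. What does not depend on them is that no listed Reach figure shows the level reached while the facilitator was at work.

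**What to change.** In sections 5.1 and 5.7:

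- Report Reach for July-December 2022 as its own period, by quarter, so that window lengths match January-March 2023.
- End the pre period at June 2022, and give dates for the start-of-facilitation rate or drop it.
- Replace the fixed active-period population with a denominator specific to each period: Veterans with a visit, or with AUDIT-C of 5 or more, in that period. Use the same choice in both sections.
- Present active versus pre, post versus active, and post versus pre descriptively. Do not label active versus pre a clean effect of facilitation, because of ramp-up and possible observation effects.
- Keep the Adoption rate during facilitation in section 5.7, so that it agrees with section 5.1.

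No new data are needed: the active months are in the extract, and extraction, cleaning and analysis are the activities still to be done. The cost is some rewording, denominators derived per period, and one more descriptive contrast to interpret.

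### The 2019-2022 baseline label overlaps the July-December 2022 facilitation months, and the time-series model has no rule for coding those months

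*Combined protocol and SAP*

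**What the plan says.** Section 5.1 (Evaluation of the Practice Facilitation Intervention) distinguishes three periods: "the pre-intervention period, the active facilitation intervention period, and the post-facilitation intervention period". For Adoption it dates the first two as "Rates of alcohol-related care pre-intervention (2019-2022), during the course of the practice facilitation intervention (July 2022-December 2022" and gives exact calendar dates for the 3- and 6-month windows that follow. Section 5.2 repeats the labels for service use: "pre-implementation (2019-2022), during (July 2022 - Dec. 2022) and post-implementation intervention (Jan 2023 - Dec. 2023".

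Section 5.7 reports Reach descriptively, "and compared pre- (2019-2022) and post-implementation (at 3- and 6-months", and mentions no active period in that comparison. For Effectiveness it specifies a "regression model with an indicator for practice facilitation (pre- vs. post-), a continuous term for time (days since practice facilitation dissemination", plus their interaction. The indicator is to capture the immediate change after the intervention, and the interaction the change in slope.

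The baselines also differ between sections. For Reach, 5.1 uses the rate when facilitation started, while 5.7 uses 2019-2022. For Adoption, 5.1 uses 2019-2022, while 5.7 uses the start of active implementation.

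**The concern.** There are two separate problems.

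The first is the label. Facilitation ran wholly inside 2022, so a baseline of 2019-2022 overlaps it on its face. No section gives the day or month on which the baseline ends, although the post-intervention windows are dated to the day. The Reach comparison in 5.7 is the most exposed, because nothing there separates the active months from the baseline.

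The second is the model. The study has three phases and the model has a two-level term. July-December 2022 must therefore be coded pre, coded post, or dropped, and the text does not choose. Counting time from dissemination suggests a break in July 2022. Describing the indicator as the change after the intervention suggests a break in January 2023. Section 5.1 describes observation in the early months and ongoing monthly improvement meetings, so a gradual build-up is plausible, and a single break handles that poorly under either coding.

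At stake is the size and direction of the level and slope estimates, which 5.1 intends as pilot data for a larger trial. An analyst could also choose the coding after seeing the data.

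**Working it through.** The plan gives no effect size, standard deviation or power figure, so there is no stated number to reproduce. The dates come from 5.1 and 5.2. The effect size, effect shapes and even screening volume are assumptions.

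**Overlap.** January 1, 2019 to December 31, 2022 is 1461 days (48 months). July 1 to December 31, 2022 is 184 days (6 months). The overlap is 184/1461 = 12.6%, or 6/48 = 12.5% in months. A baseline ending June 30, 2022 has 1461 - 184 = 1277 days (42 months).

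**Reach contrast, label read literally.** Let the true change be d and the treated share of the baseline be f = 0.126. With even volume and the full effect from July 1, 2022, the baseline rate moves by f x d, so the contrast is d(1 - 0.126) = 0.874d, a loss of 12.6%. With a linear build-up the active months carry half the effect on average, so the loss is 0.126/2 = 6.3%.

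**Time-series model.** Fit by least squares to 60 noise-free monthly means (month 0 = January 2019, 42 = July 2022, 48 = January 2023, 59 = December 2023):

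y(t) = b0 + b1 t + b2 D(t) + b3 D(t) t, with estimated effect at t = b2 + b3 t.

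D starts at month 48 if the active months are coded pre or excluded, and at month 42 if they are coded post. The assumed true effect is -0.20 AUDIT-C points, fully present by January 2023. The build-up rises in equal steps from one sixth in July to the full effect in December 2022.

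| Effect shape | Coding of active months | January 2023 | December 2023 |
|---|---|---|---|
| Step in July 2022 | pre | -0.108 | -0.078 |
| Step in July 2022 | post | -0.20 | -0.20 |
| Six-month build-up | pre | -0.145 | -0.127 |
| Six-month build-up | post | -0.154 | -0.235 |
| Onset in January 2023 | pre | -0.20 | -0.20 |
| Any of the three | excluded | -0.20 | -0.20 |

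Share of the effect lost with the active months coded pre:
- Step: (0.20 - 0.108)/0.20 = 46% in January and (0.20 - 0.078)/0.20 = 61% in December.
- Build-up: (0.20 - 0.145)/0.20 = 28% and (0.20 - 0.127)/0.20 = 37%.

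The build-up coded post shows a decline continuing through 2023, although the true effect is flat throughout that year.

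**Sensitivity.** If the build-up starts from zero in July instead, coding the active months pre gives -0.160 and -0.147, losses of 20% and 27%. A daily-grid fit with a unit effect gives level changes at the break of 0.54 (step, pre), 0.77 (build-up, pre), 0.44 (build-up, post) and 1.00 (excluded). The proportional losses do not depend on the effect size.

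**The case against.** A reader might infer that the plan uses treated time as control in the AUDIT-C model and that both its terms are therefore biased. The documents do not support that. The 2019-2022 label is attached to Adoption, service use and Reach, not to the time-series model, whose text carries no calendar dates. Counting days from dissemination is compatible with coding the active months as post. Two of the combinations above show no bias at all: a July step coded post, and a January 2023 onset coded pre.

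It is also fair to read 2019-2022 as shorthand for a baseline ending when facilitation began, since 5.1 and 5.2 list the active period beside it as a separate item. Adoption is reported for the active period separately, so the overlap matters less there. Even on the literal reading, the Reach dilution is modest and the comparison is descriptive. Section 5.1 considers a measurable clinical effect unlikely in a pilot, and 5.7 presents Effectiveness partly as a training exercise.

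All of this stands, and it limits the claim. It does not supply the missing rule. The shorthand reading is written nowhere, and neither the baseline end date nor the coding of the active months can be recovered from the text.

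**Conclusion.** The concern holds as an overlapping label and an undefined coding, not as a demonstrated bias.

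Read literally, the Reach comparison in 5.7 counts six treated months in a 48-month baseline and loses about 6-13% of the contrast, given even screening volume and an effect that builds up over the active months or is present from their start.

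For Effectiveness, the two-level model cannot represent the three periods the plan names. Under the effect shapes tried, the estimate ranges from correct, to a loss of 46-61% (July step coded pre), to a spurious continuing decline (build-up coded post). Those figures are conditional on assumed shapes and codings. Excluding the active months recovers the assumed effect in every case tried.

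The conflicting Reach and Adoption baselines are a plain inconsistency. Nothing in the documents makes the multi-year period a better comparator than the start of facilitation; that is a design choice the plan has to make and state.

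**What to change.** State the periods once and use them in 5.1, 5.2 and 5.7: Pre = January 1, 2019 to June 30, 2022; Active = July 1 to December 31, 2022; Post = January 1 to December 31, 2023.

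In the time-series model, either give the active months their own segment or exclude them from the fit. Centre post time at January 1, 2023, so that the indicator coefficient is the level change on that date, and replace the undated dissemination origin accordingly.

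Choose one baseline for Reach and one for Adoption, and make 5.1 and 5.7 agree on each.

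The cost is some date wording and either one extra phase in the model or six months lost from the fit, with slightly less precision. No new data are needed: the planned extraction covers January 2019 to December 2023, and the protocol lists extraction and analysis as still to be completed. The change should be made before the outcome data are analysed.
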